Though a rich precedent exists for utilizing recording technology in music therapy, its clinical potential and therapeutic relevance have not been systematically investigated. Kirkland & Nesbitt (2019) offer a model of therapy-oriented recording as a medium for self-reflection and personal narrative review for patients with concurrent psychiatric disorders. When framed as a mental health advocacy project to be released to the general public, recording the patient-composed song in the MTAR treatment sequence offers patients an opportunity to proactively work together in a socially supportive context to change public perception of mental illness, to refute self-relevance of stereotypes by strengthening and broadening self-concept, and empower themselves and each other with creative, expressive tools to confront and adapt to the "experience, perception, or anticipation of negative social reactions" (Livingston & Boyd, 2010) to mental illness that initiate stigma internalization.

In this study, subjects will work together with a certified music therapist (MT) in groups of 5 to 7 subjects per group to compose, rehearse, and record a song to be released to the general public for the purpose of generating anti-stigma mental health awareness. The primary objective is to reduce internalized stigma from baseline relative to the control group as measured by the 29-item Internalized Stigma of Mental Illness Inventory (ISMI; Ritsher et al., 2003). The secondary objective, examining the association between treatment effect and diagnostic category, can assist in generating hypotheses related to effective implementation. The exploratory goal of the study is to examine the potential for the treatment effect of the music therapy intervention to persist after 21 days from baseline.

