3.4. Primary Outcome Variables

ISMI score pre-treatment, ISMI score post-treatment

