4.3. Study procedures

Patients will be identified and referred upon admission to the Acute Care Unit at HMH Carrier Clinic by the treatment team (attending doctors, nurses, and social workers). All subjects who are anticipated to remain admitted to the unit for at least 7 days will be considered regardless of gender or racial/ethnic background with the exception of those less than 18 years of age.

Internalized stigma will be assessed within 3 days of admission (pretest/baseline), at ten days (posttest), and at 3 weeks from baseline (follow-up), using the Internalized Stigma of Mental Illness Inventory (Ritsher et al., 2003; Appendix 2). The ISMI is a widely-used measure with acceptable internal consistency (α = .72-.90) and test–retest reliability (r = .68-.92; Boyd et al., 2014; Chang et al., 2016). It was selected over the Perceived Devaluation

and Discrimination Scale (PDD; Link, 2987) and Self-Stigma in Mental Illness Scale (SSMOI; Tucker et al., 2013) due to concerns about internal consistency and psychometric properties of these measures (Brohan et al., 2010). Data collection will include the subject's name, diagnoses, treatment ID number, and ISMI score. Treatment effect will be measured by using a two-factor, mixed-design analysis of variance (ANOVA). A P value of less than 0.05 will be considered to indicate statistical significance.

Description of Procedures

The music therapy treatment group will utilize a certified music therapist to facilitate a series of 5 group music therapy sessions over the course of 5 to 7 consecutive weekdays. Groups will be composed of 5 to 7 patients and the MT. There is no standard number of sessions for interventions addressing internalized stigma, and the available literature varies from one session in a single day to twenty sessions over a period of months. Since the average length of stay for acute care unit patients is 7 to 10 days, 5 sessions is the maximum feasible number of sessions to complete the treatment sequence for shorter stays. Though patients typically receive daily music therapy groups as part of the standard of care, this study improves upon the standard of care by providing a protocolized intervention sequence targeted at reducing internalized stigma of mental illness.

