5.8. Statistical Method

5.8.1. Sample size calculation and justification

Based on power analysis (power=80%, see assumptions below) and the design of the study, 50 patients will be accrued to each group (n=100).

The study has a two-factor repeated-measures ANO VA design. For the power analysis, the assumption of sphericity will be made (*epsilon* = 1). Sphericity is the condition where the variances of the differences between all combinations of related groups (levels) are equal.

Assumptions and parameters of power analysis:

Sphericity: *epsilon* = 1 Type I error: *alpha* = 0.05 Type II error: *beta* = 0.2

Required power: power = 100(1 - B) = 80%Effect size: f = 0.1, 0.25, 0.33, 0.4, 0.8

Cohen's effect size for F test, 0.1 ("small"), 0.25 ("medium"), 0.33, and 0.4 ("large"). Effect

size of 0.33 was used.

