5.8.2. Statistical Analysis Plan

Primary Analysis

Treatment effect on the primary dependent variable (ISMI score) will be measured by using a two-factor repeated-measures analysis of variance (ANOVA). A P value of less than 0.05 will be considered to indicate statistical significance.

Secondary Analysis

Treatment effect on the secondary dependent variables (diagnosis category) will be measured by using a two-factor repeated-measures analysis of variance (ANOVA). A P value of less than 0.05 will be considered to indicate statistical significance.

Exploratory Analysis

Treatment effect on the exploratory variable (ISMI score 3 weeks after baseline) will be measured by using a two-factor repeated-measures analysis of variance (ANOVA). A P value of less than 0.05 will be considered to indicate statistical significance.

6 - Trial Administration

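### Baseline-adjusted post-test ISMI would be a modestly more precise primary analysis than the group-by-time ANOVA test that the plan implies

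*Combined protocol and SAP*

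**What the plan says.** The primary analysis in 5.8.2 reads: "Treatment effect on the primary dependent variable (ISMI score) will be measured by using a two-factor repeated-measures analysis of variance (ANOVA"), with the criterion "A P value of less than 0.05 will be considered to indicate statistical significance". Section 4.3 describes the same analysis slightly differently: "Treatment effect will be measured by using a two-factor, mixed-design analysis of variance (ANOVA"). Neither place lists the factors, the levels of time or the F test that decides the trial, and neither uses the pre-test as a covariate.

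Other sections indicate what is meant. The Introduction states: "The primary objective is to reduce internalized stigma from baseline relative to the control group". The hypothesis in 3.2 is framed the same way. Section 3.4 gives the primary outcome variables as "ISMI score pre-treatment, ISMI score post-treatment", while the 3-week score is the exploratory outcome in 3.8. Together these point to the group-by-time interaction over two time points.

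Section 5.8.1 describes the design as two-factor repeated-measures ANOVA and sets 50 patients per group at f = 0.33. It gives no ISMI standard deviation and no pre-post correlation. The only correlation in the documents is the test-retest figure in 4.3 and 5.5: "reliability (r = .68-.92".

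**The concern.** With two time points, the group-by-time F test is the square of the t-test comparing mean change between arms. A change score subtracts the pre-test with weight 1, whatever its actual correlation with the post-test. A regression of post-test on arm and pre-test estimates that weight from the data. When r is below 1 and allocation is random, the fixed weight adds noise to the primary comparison.

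What is at stake is precision. The pre-test is taken from every enrolled patient under 4.3, and the implied test does not use all the information in it.

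**Working it through.** **The plan's own figure.** Section 5.8.1 gives 100 patients for 80% power at f = 0.33 and alpha 0.05. With two equal groups, f = 0.33 corresponds to d = 2 × 0.33 = 0.66. A plain two-group F test then needs 76 in total, and 100 gives 90.4% power. The figure of 100 is therefore not reproduced. The ANOVA term, correlation and dropout behind it are not given, so it is unexplained rather than shown to be too small. That is a separate matter. The check below takes 50 per arm as stated.

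**Inputs.** 50 per arm (5.8.1); alpha 0.05, taken as two-sided; pre-test and post-test SD both set to 1 (assumption); r = .68 to .92, borrowed from the test-retest range in 4.3 (assumption); patients independent and all followed to post-test (assumption).

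**Formulas.**
- Variance per patient, change score: 1 + 1 − 2r = 2(1 − r).
- Variance per patient, post-test adjusted for pre-test (ANCOVA): 1 − r².
- Ratio of ANCOVA to change: (1 − r²) / [2(1 − r)] = (1 + r)/2.
- Standard error of the arm difference: √(2 × variance / 50).
- Detectable difference at 80% power, normal approximation: (1.960 + 0.842) × SE = 2.802 × SE.

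**At r = .68.**
- Change: variance 2 × 0.32 = 0.64; SE = √(1.28/50) = 0.160; detectable 2.802 × 0.160 = 0.45 SD.
- ANCOVA: variance 1 − 0.4624 = 0.5376; SE = √(1.0752/50) = 0.147; detectable 2.802 × 0.1466 = 0.41 SD.
- Ratio: 1.68/2 = 0.84, so 84 patients with ANCOVA match 100 with change scores.

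**At r = .92.**
- Change: variance 0.16; SE 0.080; detectable 0.22 SD.
- ANCOVA: variance 0.1536; SE 0.078; detectable 0.22 SD.
- Ratio: 1.92/2 = 0.96.

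**Power at 50 per arm** (noncentral t):

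| True post-test difference | r | Group by time (change) | ANCOVA |
|---|---|---|---|
| 0.40 SD | .68 | 69.7% | 77.1% |
| 0.40 SD | .80 | 87.9% | 91.0% |
| 0.40 SD | .92 | 99.9% | 99.9% |
| 0.66 SD | .68 | 98.3% | 99.4% |

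The last row takes f = 0.33 to mean a post-test difference of 0.66 SD. Section 5.8.1 does not tie f to any term.

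**Simulation check.** With 4,000 runs, a true difference of 0.40 SD and r = .68, the SE was 0.144 for ANCOVA and 0.158 for change. Power was 77.5% and 70.3%. Both estimates centred on 0.40.

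**Baseline differences between wings.** If the arms differ by D SD at pre-test, the two estimates differ by D − rD = (1 − r) × D. For D = 0.3 this is 0.32 × 0.3 = 0.10 SD at r = .68 and 0.08 × 0.3 = 0.02 SD at r = .92.

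**The case against.** The strongest reply is that the implied test is standard and valid, and that a one-line clarification naming group by time would complete the plan. At d = 0.66 and r = .68 or above, both tests exceed 98% power before clustering and dropout, so the swap changes little. This stands as a limit on the size of the point. It does not remove the gain at smaller effects or lower correlations.

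The second reply concerns the design. Sections 4.1 and 5.4 allocate conditions to two wings rather than to patients, and 4.3 takes the pre-test after enrolment and consent. A reader might infer that the change score is biased under baseline imbalance and that ANCOVA cures this. The documents do not support that as a general claim. If the imbalance is chance at patient level, the change score is off by (1 − r) × D. If one wing is stably higher by D at both visits, the change score is right and ANCOVA is off by the same amount. Neither is protected from selection by wing. The two analyses therefore need not answer the same question here. This objection stands, and it is why the change analysis should remain as a sensitivity analysis.

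A reader might also infer that the group main effect could serve as the treatment test, since 5.8.2 names no term. That test averages in the pre-test, and its power at d = 0.66 and r = .68 would be only 43.0%. The stated aim, "reduce internalized stigma from baseline relative to the control group", together with 3.2 and 3.4, points to the interaction, and no section proposes the main effect. The term is unstated, but it can be inferred.

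Finally, the sphericity assumption in 5.8.1 is automatic with two time levels, which might suggest that three were intended. Sections 3.4 and 3.8 place only pre-test and post-test in the primary outcome. Stating the levels would settle it.

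**Conclusion.** The point holds as a worthwhile but modest improvement to the primary analysis. Under random allocation, adjusting post-test ISMI for pre-test ISMI reduces the variance of the treatment comparison to between 0.84 (r = .68) and 0.96 (r = .92) of that of the implied group-by-time test. The detectable difference at r = .68 falls from about 0.45 to 0.41 SD; at r = .92 the gain is near nil.

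These figures assume that test-retest reliability stands in for the pre-post correlation, that the SDs at the two visits are equal, and that patients are independent with no dropout. Reliability is only a proxy, and the correlation over an acute stay could be lower. At r = .50, which is outside the quoted range, the ratio would be 0.75.

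The finding does not show that the trial is underpowered, that the planned ANOVA is invalid, or that ANCOVA resolves wing selection or clustering.

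**What to change.** In 5.8.2, replace the primary analysis sentence with text to this effect: the primary treatment effect is the arm coefficient from a linear model of post-test ISMI on arm and pre-test ISMI, reported as an adjusted mean difference with 95% CI and p-value; only pre-test and post-test scores enter this analysis. Add that the group-by-time (change-score) comparison over the same two visits will be reported as a sensitivity analysis, and that any divergence will be read against the observed baseline difference between arms.

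Bring 4.3 and the design description in 5.8.1 into line. How to handle clustering by wing or therapy group is a separate question, and this wording does not settle it.

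The change needs no new data and no extra patients. It costs one error degree of freedom (97 instead of 98 with 100 patients) and the rewording of three sections.

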CLINICAL STUDY PROTOCOL

The Effect of a Group Music Therapy Advocacy Recording Intervention (MTAR) on Internalized Stigma in Adult Psychiatric Inpatients in Acute Care

10/20/2022

version 1.03

Study Personnel

PI:

[name], MT-BC Creative Art Therapist Clinical Social Services Hackensack Meridian Health Carrier Clinic [name] Office: [contact]

[contact]

Statistical support:

[name] Research Biostatistician Office of Clinical Research Administration Hackensack Meridian Health

Protocol Development support:

[name], MS, PhD Manager, Investigator Initiated Research Program HMH REDCap Administrator Office of Research Administration Hackensack Meridian Health

Abbreviations

Abbreviation	Explanation
ACU APA DSM-5	Acute Care Unit American Psychiatric Association Diagnostic and Statistical Manual of Mental Disorders (5th ed.; American Psychiatric Association, 2013)
HMHCC ISMI MT MTAR	Hackensack Meridian Health Carrier Clinic Internalized Stigma of Mental Illness Inventory Music Therapist or Music Therapy Music Therapy Advocacy Recording

Summary

The primary objective of this study is to determine the effect of a systematic music therapy intervention on internalized stigma of mental illness. The secondary objective is to evaluate the potential for the treatment effect to vary across subject diagnostic categories. This study will also examine the ability of the treatment effect to persist after 3 weeks as an exploratory objective.

Data collection will be conducted in the Acute Care Unit (ACU) of Hackensack Meridian Health Carrier Clinic (HMHCC) over a period of ten months. Subjects will be drawn from the pool of patients admitted to the HMHCC ACU during that time. Adults aged 18-65 with severe mental illness with a diagnosis of bipolar or a related disorder, depressive or anxiety disorder, or schizophrenia spectrum or other psychotic disorders as defined by the DSM-5 (5th ed.; American Psychiatric Association, 2013), of prolonged duration with a significant degree of disability or social dysfunction (Ruggeri et al., 2000) are eligible to participate. Eligible participants must be able to provide informed consent as determined by the doctor.

1 – Introduction

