The use of recording technology to address internalized stigma is a novel approach. A qualitative music therapy study based on a community music therapy approach (Solli & Rolvsjord, 2015) which included recording, mixing, and producing music, subjects emphasized that music therapy "represented freedom from illness, stigma, and treatment". This suggests that a music therapy recording session can provide a locus for transforming a participant's illness identity. Using recording technology creates the opportunity to utilize the public relations and social media infrastructure of the hospital to to promulgate the work as part of a mental health awareness project. Participants' belief in their potential to effect large-scale societal change via musical expression of their personal experiences is the central mechanism for instilling feelings of empowerment and motivation in this study.

"The Stigma Blues" (Silverman, 2013) Characteristic	MTAR Characteristic	Rationale of Divergence
Single-session intervention	Four-phase treatment sequence over five sessions	Build trust, group cohesion, engagement with the musical process
Blues format	Open musical format	Broad scope of musical

		expression
No advocacy component	Advocacy-based	Identity transformation through empowerment
MT performs the music	Subjects rehearse and perform the music	Identity transformation through competence and mastery
No recording component	Includes Recording and Review Phases	Extend treatment effect by monumentalizing the work for reflection and insight
Demographic data (diagnosis) not collected	Demographic data (diagnosis) collected	Investigate potential relationships between treatment effect and diagnoses to inform future developments and implementation

Table 3. Comparison of "The Stigma Blues" (Silverman, 2013) and MTAR Characteristics and Clinical Rationale of Divergence

Using recording technology creates a record of subjects' achievement that can be accessed at any time in the future and serve as a post-inpatient treatment reinforcement of an empowered identity, potentially extending the treatment effect. MTAR's actual capacity to induce systemic change is out of scope for this study.

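### Section 5.8.2 makes diagnosis the outcome of the secondary analysis and names no term that tests whether the treatment effect varies by diagnosis

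*Combined protocol and SAP*

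**What the plan says.** The objective is worded in two ways. The Summary wants to "evaluate the potential for the treatment effect to vary across subject diagnostic categories". The Introduction describes it as "examining the association between treatment effect and diagnostic category, can assist in generating hypotheses related to effective implementation". Table 3 in section 2.1 gives the same reason for collecting diagnosis: "Investigate potential relationships between treatment effect and diagnoses to inform future developments and implementation". Section 3.5 opens with a treatment aim, reducing stigma across diagnostic categories, but then describes only a comparison of ISMI scores between diagnostic groups. Section 3.6 lists the ISMI scores and the diagnostic categories together as secondary outcome variables.

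The analysis is one sentence in section 5.8.2: "Treatment effect on the secondary dependent variables (diagnosis category) will be measured by using a two-factor repeated-measures analysis of variance (ANOVA"). The primary and exploratory analyses carry the same model label. Section 4.3 says "Treatment effect will be measured by using a two-factor, mixed-design analysis of variance (ANOVA"), and section 5.8.1 begins "The study has a two-factor repeated-measures" and applies that label to the whole study. No section names the two factors, a third factor, an arm-by-diagnosis term or a subgroup contrast.

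Section 5.6 takes diagnoses from the medical chart. Appendix 1 lists diagnostic category once, with no time point, and lists ISMI at three.

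**The concern.** There are two faults. First, the stated response is not a possible one. Diagnosis is a category, not a repeated numeric measure, and it is not something the intervention is meant to change.

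Second, putting ISMI in its place does not complete the specification. Asking whether a treatment effect varies by diagnosis requires arm and diagnosis in the same model, with their interaction tested. If time is one of two factors, only one between-patient factor is left. Arm by time has no diagnosis term, and diagnosis by time has no arm term.

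At stake is the only stated secondary objective, to which section 5.8.2 attaches a 0.05 significance threshold. The analyst would have to choose the model, possibly after seeing the data. At least one choice that section 3.5 allows answers a different question, namely whether patients with different diagnoses change differently whatever their arm. A significant result there could be reported as variation in the effect of the music therapy.

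**Working it through.** **The plan's own figure.** The secondary analysis has no sample-size figure of its own. Section 5.8.1 gives 100 patients (50 per group) for the study. A plain two-group F test at f = 0.33 with noncentrality N × f² needs 76 in total, and 100 gives about 90% power. The correlation, number of measurements, tested term and dropout are not stated, so 100 cannot be called wrong. Nothing below depends on it beyond the approximate group size.

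**What each candidate model contains, with ISMI as response.**

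| Model | Arm-by-diagnosis term? |
|---|---|
| Arm × time | No; diagnosis absent |
| Diagnosis × time (one reading of 3.5) | No; arm absent |
| Arm × diagnosis on change scores | Yes, but no section says this is meant |
| Arm × diagnosis × time | Yes, but this has three factors |

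**Inputs for the illustration.** From the documents: f = 0.33 (section 5.8.1: "size of 0.33 was used"), alpha 0.05, about 50 per arm, and test–retest "reliability (r = .68-.92") from section 4.3. Assumed, because the documents do not give them: four equal categories with 12 per arm in each (96 patients), no clustering, no dropout, natural change that rises by a fixed step from one category to the next, and the test–retest range standing in for the pre–post correlation. The benefit is identical in every category.

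**Benefit.** For two equal groups d = 2f = 2 × 0.33 = 0.66. The SD that f refers to is not stated, so two scales are used.
- Scale A: 0.66 SD of the pre–post change.
- Scale B: 0.66 SD of the score. With equal SDs, the SD of change is √(2(1−r)) score SDs. At r = .68 this is √0.64 = 0.80, so the benefit is 0.66/0.80 = 0.825 SD of change. At r = .92 it is √0.16 = 0.40, so the benefit is 0.66/0.40 = 1.65.

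**Diagnosis × time.** Over two time points this is a one-way ANOVA of change on diagnosis. The table gives the proportion significant in 20,000 simulated trials per scenario:

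| Step in natural change per category (SD of change) | 0 | 0.1 | 0.2 | 0.3 |
|---|---|---|---|---|
| Scale A | 3% | 10% | 35% | 72% |
| Scale B, r = .68 | 3% | 8% | 31% | 70% |
| Scale B, r = .92 | 0.4% | 2% | 13% | 44% |
| Arm × diagnosis, all scenarios | about 5% | about 5% | about 5% | about 5% |

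The rates fall as the benefit grows because the unmodelled arm effect enters the residual. With five equal categories of 10 per arm, steps of 0.1, 0.2 and 0.3 give 12%, 51% and 91% on scale A and 2%, 21% and 68% at r = .92. With 20/14/12/4 per arm they give 8%, 27% and 61%, and 2%, 9% and 33%.

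**Power of the correct term.** Suppose the benefit b (in SDs of change) is present in two of the four categories. Each category's effect then lies b/2 from the mean effect, and the noncentrality is 4 × (12/2) × (b/2)² = 24 × (b/2)², on F(3, 88).
- Scale A: 24 × 0.33² = 2.61, power 23%.
- Scale B, r = .68: 24 × 0.4125² = 4.08, power 35%.
- Scale B, r = .92: 24 × 0.825² = 16.3, power 93%.

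**Precision.** The 95% half-width for the difference in effect between two categories is 1.96 × √(4/12) = 1.13 SD of change. That is 1.13/0.66 = 1.7 times the assumed benefit on scale A, and 1.4 to 0.7 times on scale B.

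**The case against.** The strongest reply is that the dependent-variable wording is a slip. Section 3.5 compares ISMI scores and section 3.6 lists ISMI first, so any analyst would take ISMI as the response. That is probably what would happen, but section 3.6 repeats the slip and the correction still leaves the factors unnamed.

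It can also be said that the missing interaction is an inference. This stands in part. The factors are never named, the mixed-design sentence in section 4.3 is general, and the secondary sentence mentions treatment and diagnosis together. A reader might infer that the plan definitely excludes an arm-by-diagnosis test, but the documents do not go that far. They show only that no such term is stated and that the most natural reading of their label leaves it out. Likewise, section 3.5 does not plainly prescribe diagnosis by time, because its first sentence is a treatment aim.

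Two further inferences should be resisted. A reader might take diagnosis to be a baseline item, but neither section 5.6 nor Appendix 1 says when it is recorded. A reader might also expect separate tests within each diagnosis and the misleading mixed patterns these produce, but no section proposes that analysis, so it is not counted here.

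Finally, the illustration rests on an invented diagnostic mix and invented natural change. This is true, and the width of the range shows that the documents do not determine the size of the harm.

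**Conclusion.** The secondary analysis is wrong as written, not merely short of detail. Its stated response is impossible, and it names no term that answers the objective in the Summary and Introduction. It should be corrected, but the reach is limited: the primary analysis is untouched, and the Introduction calls this objective hypothesis-generating.

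The size of the possible error depends on the model chosen and on unknowns. If diagnosis by time were used and natural change differed by 0.1 to 0.3 SD of change per category, about 2% to 72% of trials with an identical treatment effect would be significant under four equal categories, against about 5% for arm by diagnosis. With no natural difference there is no inflation (0.4% to 3%). These figures ignore clustering and dropout.

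**What to change.** In section 5.8.2, state the following.
- The secondary outcome is ISMI at post-test.
- Diagnosis category is a factor, not an outcome. It is taken from the chart as recorded at enrolment, with one primary category per patient. Sections 4.3 and 5.6 speak of diagnoses in the plural, so without such a rule the factor is undefined.
- The tested term is arm × diagnosis in a model of post-test ISMI on baseline ISMI, arm, diagnosis and arm × diagnosis. If the ANOVA is kept, the corresponding term is arm × diagnosis × time over pre-test and post-test.
- The MTAR–control difference is reported with a 95% confidence interval in each category, labelled hypothesis-generating.
- A non-significant interaction is not read as support for the hypothesis in section 3.2 that the effect holds whatever the diagnosis.

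Reword sections 3.5 and 3.6 to match the Summary's objective. Reconcile the no-diagnosis level in sections 3.5 and 3.6 and Appendix 1 with the Summary, which requires one of the listed diagnoses.

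The cost is a wording amendment through the IRB route in section 6.2, plus a rule for assigning one category. ISMI and diagnosis are already collected, and arm is known from the wing. The drawback is that category estimates will be imprecise and interaction power may be low: about 23% if the benefit is 0.66 SD of change and present in half the categories, and 35% to 93% if 0.66 refers to the score SD.

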3.2. Hypothesis

Adult psychiatric inpatients on an acute care unit who participate in music therapy groups focused on writing, recording, and releasing music to the general public for the purpose of mental health advocacy will report less internalized stigma from baseline relative to the control group upon completion of the treatment sequence, regardless of subject diagnosis. The effect will persist when measured at 3-weeks post-baseline.

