4.1.1 Study Duration

The proposed study duration is one year, with eight months allotted for data collection, and four months allotted for data analysis. Subjects will be involved for a period of 21 days, including follow-up data collection (See Table 4). Results of this study can help inform the feasibility of collecting follow-up data from this population, as patient adherence to aftercare plans can be unpredictable.

Day	Treatment Group	Control Group

1-3	Enrollment, Pre- Test/Baseline	Enrollment, Pre-Test
4-10	Treatment Sequence	No Treatment Sequence
8-10	Post-Test	Post-Test
21	Follow-up data collected	Follow-up data collected

Table 4. Study Timeline Per Cohort

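### The exploratory 3-week analysis names a repeated-measures ANOVA but no time levels, week-3 contrast or missing-data method, so it may not test persistence and would by default drop anyone not reached at follow-up

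*Combined protocol and SAP*

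**What the plan says.** Section 3.2 makes persistence part of the hypothesis: "The effect will persist when measured at 3-weeks post-baseline". Its only planned analysis is the exploratory paragraph of section 5.8.2. The target there is "Treatment effect on the exploratory variable (ISMI score 3 weeks after baseline", and the method named is a two-factor repeated-measures ANOVA, with the rule that "A P value of less than 0.05 will be considered to indicate statistical significance". That section does not say which visits are the levels of the time factor, which contrast answers the question, who is analysed, how missing scores are handled, or whether any sphericity correction is used.

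ISMI is measured three times (sections 4.1 and 4.1.1, Table 4): days 1-3, about days 8-10, and day 21. Section 5.7 allows the last assessment by phone after discharge. Section 4.1.1 warns that "patient adherence to aftercare plans can be unpredictable". Section 5.2 stops data collection for subjects discharged or noncompliant during treatment, and keeps what was already collected. No loss rate is given.

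Sphericity is mentioned once, in section 5.8.1: "For the power analysis, the assumption of sphericity will be made".

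**The concern.** Persistence is a statement about one quantity: the arm difference in change from baseline to week 3. An omnibus arm-by-time test over three visits asks something else, namely whether the arm difference varies at all over time. It can be significant because of the post-test alone, so an effect that has vanished by week 3 could be reported as persistent.

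The classical ANOVA also needs a complete row per subject. After discharge, those reached may differ from those not reached, and differently by arm. The claim would then rest on a selected subset, with the post-test scores of the others unused. A three-visit F test without correction also assumes equal variances of all pairwise differences, which is unlikely if correlation fades with time.

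**Working it through.** **Plan's own figure.** Section 5.8.1 gives 50 per group for 80% power at f = 0.33. For two groups d = 2f = 0.66, and n per group = 2(1.960 + 0.842)²/0.66² = 15.70/0.4356 = 36.0, or 37 with the t correction. Fifty per group gives about 91% power. The stated 100 is therefore not reproduced; an unstated 25% loss would give it (37/0.75 = 49.3, so 50). Nothing below depends on this. I use 50 per arm, and 0.66 SD as the post-test effect.

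**Assumed inputs.** Visits at days 2, 9 and 21 (from Table 4). Correlation r^(gap/7) with r = .68 to .92, borrowing the test-retest range in sections 4.3 and 5.5. The documents give no between-visit correlation for planning.

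**1. Does the omnibus test isolate persistence?** Let δ1, δ2, δ3 be the arm differences at the three visits. The interaction null is δ1 = δ2 = δ3; persistence concerns δ3 − δ1. Take δ = (0, −0.66, 0): the null is false, yet δ3 − δ1 = 0. Results from 20,000 trials per setting, over the range of r:

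| True effect at post-test / week 3 | Omnibus arm × time P<0.05 | Week-3 versus baseline contrast P<0.05 |
|---|---|---|
| 0.66 SD / 0 | 97-100% | about 5% |
| 0.33 SD / 0 | about 40% to over 95% | about 5% |

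**2. Sphericity, three visits.** For r = .80 the correlations are .800 (days 2-9), .682 (9-21) and .546 (2-21). The difference variances 2(1 − ρ) are 0.400, 0.636 and 0.909, which are not equal. With V the covariance of two orthonormal time contrasts, ε = (tr V)²/(2 tr V²).
- tr V = (0.400 + 0.636 + 0.909)/3 = 0.648.
- The covariance of the two changes from baseline is (0.400 + 0.909 − 0.636)/2 = 0.3365.
- det V = (0.400 × 0.909 − 0.3365²)/3 = 0.0835.
- tr V² = 0.648² − 2 × 0.0835 = 0.253.
- ε = 0.420/0.506 = 0.83.

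| r per 7 days | ε | Type I error, uncorrected (40,000 runs) |
|---|---|---|
| .68 | 0.87 | 5.6% |
| .80 | 0.83 | 5.8% |
| .92 | 0.79 | 6.0% |

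Repeat runs lie around 5.6-6.1%. At the lowest possible ε of 0.5 the bound is P(F(1,98) > F.95(2,196)) = 8.4%. A Greenhouse-Geisser correction gave 4.8-5.1% throughout.

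**3. Loss at week 3.** Complete-case change from baseline was compared with likelihood estimation (free means and covariance per arm). The figures are bias in SD units; every loss rate and mechanism is an assumption.

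| Loss mechanism (nominal loss rate) | Complete-case | Likelihood |
|---|---|---|
| Completely at random (20% / 40%) | 0.00 / 0.00 | 0.00 / 0.00 |
| Depends on post-test score, same direction in both arms (20% / 40%) | −0.01 / −0.02 | 0.00 / −0.01 |
| Depends on post-test score, opposite directions by arm (20% / 40%) | +0.05 / +0.07 | +0.01 / 0.00 |
| Depends on post-minus-pre change, one arm only or opposite by arm (about 30%) | 0.10-0.27 (absolute) | within 0.01 |
| Depends on the unseen week-3 score, opposite by arm (20% / 40%) | −0.17 / −0.30 | −0.21 / −0.37 |

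A further arm-opposed setting with loss driven by observed scores gave 0.15-0.32 for complete cases and about 0 for likelihood. Precision also suffers. Under random loss of 40% the standard deviations of the estimates were 0.245 and 0.229, so complete-case variance is (0.245/0.229)² = 1.14 times as large; at 20% loss it is (0.209/0.203)² = 1.06 times.

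**4. The two-visit reading.** With baseline and week 3 only, the arm-by-time term is the week-3 contrast and ε = 1 by construction. Steps 1 and 2 then fall away. Step 3 remains, and the post-test scores are not used at all.

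**5. When is week 3?** Sections 3.2, 4.1, 5.5 and 5.8.2 count from baseline (day 21 in Table 4). Sections 3.6 to 3.8 count from the end of treatment. With the post-test on days 8-10, that is days 8 + 21 = 29 to 10 + 21 = 31. These are different assessments.

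**The case against.** The strongest reply is that much of this is inferred. Four stronger readings are tempting.

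- *That the plan prescribes a complete-case analysis.* It does not use the term, and it says that collected data are kept. Listwise deletion is what the classical method does unless told otherwise. The gap is the silence on missing data.
- *That the analysis is run under sphericity.* "the assumption of sphericity will be made" applies to the power calculation only. No correction is named, but none is ruled out.
- *That three visits enter the model.* Section 5.8.2 gives no time levels, and section 3.8 lists only the 3-week score, so a baseline versus week-3 ANOVA is an equally available reading. Under it, the sphericity and mixing points disappear.
- *That a mixed model cures drop-out bias and error inflation.* It removes the bias only under missing-at-random; when loss depended on the unseen score, likelihood was somewhat worse than complete cases. Large-sample Wald tests from an unstructured model at this size also run slightly above 5% (about 5.6-5.9% for the interaction). A random-intercept model would bring compound symmetry back.

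These replies stand, and the point is limited to match. They do not supply a contrast or a missing-data rule. The objective is also exploratory, and section 4.1.1 treats follow-up partly as a feasibility question, which limits the consequence.

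**Conclusion.** The concern holds as a specification gap with two consequences. First, subjects without a week-3 score would by default be lost. That costs precision under any mechanism, and it biases the estimate if loss depends on earlier scores differently by arm. The 0.05 to 0.32 SD found here illustrates the mechanism and is not a forecast, because the documents give neither a rate nor a mechanism. Second, if three visits are used, the omnibus test does not test the persistence claim in section 3.2.

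Non-sphericity is minor: about 5.6-6.1% under serial correlation of .68-.92 per 7 days, and only under the three-visit reading. A reader might infer a seriously inflated error rate; the figures do not support that, and a Greenhouse-Geisser correction alone would deal with it. The case for changing the model rests on the contrast and the missing data. The primary analysis is not touched by this point.

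**What to change.** 1. Reconcile the follow-up time across sections 3.2, 3.6-3.8, 4.1, 5.5 and 5.8.2, since the estimand depends on it.
2. In section 5.8.2, replace the exploratory ANOVA with a linear mixed model of ISMI at all visits: arm, visit and arm × visit, unstructured covariance, and small-sample degrees of freedom such as Kenward-Roger. Include every participant with a baseline and any later score.
3. Name the week-3 arm contrast against baseline, with its 95% CI, as the persistence estimate. Do not use the omnibus interaction for that claim.
4. State that the estimate is valid under missing-at-random. Add a simple MNAR sensitivity analysis, for example shifting the unobserved week-3 values by a stated range in each arm. Report the numbers lost by arm.
5. State as a limitation that the interval does not account for assignment by wing or for the therapy groups of 5 to 7. Subjects dropped during treatment under section 5.2 before any post-test have no later score and remain outside this analysis.

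The cost is SAP wording and standard software. No new data are needed.
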